Older people are included when they meet the following criteria: they are 65 years of age or older, home-dwelling within the selected regions, they are Dutch speaking, and they did not have a dental check-up in the last 12 months. (19) By home-dwelling, we mean anyone who does not reside 24/7 in a residential care facility. If it concerns a couple, only one person can participate. Participants should have sufficient cognitive ability to answer the questions. If we ask the questions and find that the older person is unable to answer them adequately due to cognitive impairment, he or she will not be included in the study.

[11a] Interventions

After filling out the interview based questionnaire (see Appendix), the participants will be randomized between the control group and the intervention group. This will ensure that there are equal numbers of frail people in both groups.

The participants in the intervention group will receive an oral examination. Subsequently, information about any identified problem will be given. Lastly, participants will receive a referral letter for their dentist and a report for the general practitioner. If the participants don't have a regular dentist, they will also be given a list with contact information of dentists in the area.

Both the intervention and the control group will receive a flyer with oral hygiene instructions adapted to their needs and if necessary a list with contact information of dentist in the area. These flyers are evidence-based brochures compiled by the Flemish institute of oral health ("Gezonde Mond") on performing good oral hygiene.

[11b] Interventions - modifications

If an elderly person is randomized into the intervention group but refuses to have an oral examination, this will be noted.

If an elderly person in the control group asks for an oral examination because of a particular problem, the elderly person will be given the advice to contact a dentist.

[11c] Interventions – adherence

At the end of the initial contact, participants will be reminded that they will receive a phone call after 4 months. All participants will receive a pen with the logo of Gerodent PLUS as a gift.

[11d] Interventions – concomitant care

No concomitant care is prohibited to the participants. The intent of the study is to examine whether older people find access to regular care due to our intervention.

[12] Outcomes

Primary Outcome Measures

[figure not shown]

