Participants will be contacted 4 months after the initial contact by telephone to ask if they contacted a dental professional since the first contact. We will make four attempts to contact them, two in the

morning and two in the afternoon. Contact information of partner or caregiver will also be included, in case the participant cannot be reached.

If the older person has contacted a dental professional within 4 months of our initial contact, then this is considered a success. Due to a shortage of dental professionals in Flanders, there is often a fairly long waiting period before a patient can get an appointment. In addition, many professionals have implemented a patient stop. So we want to give the elders enough time to find a dental professional. Differences in proportions will be reported.

[figure not shown]
| | Intervention group | Control group |
|---|--------------------|---------------|
| Contacted a dentist within 4 months | | |
| Not contacted a dentist within 4 months | | |

[13] Participant timeline

[14] Sample size

We expect to activate 30% of the participants in the intervention group; in the control group, we expect a maximum of 10%. To detect a mean difference of 20% with equal allocation to both groups would require 129 persons in total. To allow for 33% drop-out, 194 persons will be recruited.

[15] Recruitment

Service centers within the RITS and Scheldekracht primary care zones will be asked if they are willing to participate in the study. A date will be arranged with the interested centers when the study can take place in their facilities.

Organizations and other local initiatives will also be contacted to spread our call for participation in the study. Older people will be able to sign up at a participating service center to participate in the study.

Furthermore, home nursing and home care service organizations in the region have agreed to assist with participant recruitment.

Methods: Assignment of interventions

Allocation

[16a] Sequence generation

Participants will be randomly assigned to either control or intervention group with a 1:1 allocation. Randomization will be stratified by frailty. Random permuted blocks will be created using SAS v9.4 with variable sizes to avoid that the treatment allocation can be predicted. For practical reasons block size will vary between 8 and 12.

[16b] Allocation concealment mechanism and [16c] Implementation

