- At the end of the initial contact, participants will be reminded that they will be called again 4 months later. Contact information for a partner, child or caregiver will also be noted. If a participant indicates they prefer to receive a letter, the home address will be noted.
- All participants will receive a pen with the logo of Gerodent PLUS as a gift.
- A 33% drop-out rate was taken into account when calculating the sample size.

- Refusal of the oral examination will be noted. However, since we are working from the intention to treat principle, the participant will remain in the intervention group.

[19] Data management

Data will be collected exclusively electronically through REDCap. REDCap is a secure web application for building and managing online surveys and databases. The type of activity that an individual user may undertake is regulated by the privileges associated with his/her account.

Once all data are collected, a copy of REDCap will be kept on the secure servers of Ghent University. Only members of the research team will have access to the data. If needed, data will be transferred using a Secure File Transfer platform, Belnet Filesender.

Statistical methods

[20a] Statistical methods for primary and secondary outcomes

Two weeks after the last telephone questionnaire was scheduled, we will end the data collection and the statistical analysis will be executed. The intervention group will be compared against the control group for having consulted a dentist within 4 months after the initial contact. Differences in proportions will be reported, logistic regression models will be used.

[20b] Methods for additional analyses (e.g. subgroup analyses)

[figure not shown]
Subgroup analyses will be purely exploratory:

- Impact of age on outcome
- Impact of gender on outcome
- Impact of education on outcome
- Impact of financial situation on outcome
- Impact of frailty on outcome.
- Impact of whether participant is dentate or edentulous on outcome.
- Impact of whether participant experienced oral problems the previous 6 months on outcome.

[20c] Methods in analysis to handle protocol non-adherence and any statistical methods to handle missing data

All randomized participants will be included in the “intention to treat”-analysis. This means that a participant allocated to the intervention group, who refuses an oral examination will remain in the intervention group.

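### Randomisation is stratified by frailty, but the primary analysis names no stratum and the per-arm imputation does not mention frailty (minor)

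*Combined protocol and SAP*

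**What the plan says.** Section [16a] of the combined protocol and SAP states: "Randomization will be stratified by frailty". Section [11a] gives the aim: "This will ensure that there are equal numbers of frail people in both groups". It also fixes the order of events: "After filling out the interview based questionnaire (see Appendix), the participants will be randomized between the control group and the intervention group". Section [16b] adds that the allocation is released only once the questionnaire is complete. Frailty is therefore known for everyone randomised, including people who cannot be reached at 4 months.

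On the analysis:

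- Section [20a] compares the two arms and continues: "Differences in proportions will be reported, logistic regression models will be used". It names no covariate or stratum.
- Section [12] shows a two-by-two table by arm, with "Not contacted a dentist within 4 months" as its second row and no split by frailty.
- Section [20b] lists frailty among several factors under the statement "Subgroup analyses will be purely exploratory".
- Section [20c] imputes missing outcomes separately in each arm. It mentions natural teeth and the timing of the last dental visit, and says that more variables may be added. Frailty is neither named nor ruled out.

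**The concern.** Frailty is the only factor that the design chose to balance, and the analysis plan does not carry it forward. As [20a] stands, one analyst could fit arm alone and another could fit arm plus frailty, and both would comply. That choice should be made before outcomes are seen.

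Two things are at stake. If frailty predicts dental contact, an analysis by stratum recovers precision that the stratified design makes available. And [14] allows for one third of participants being lost. If frail people are harder to reach and also differ in how often they contact a dentist, an imputation model without frailty fills in the missing outcomes from a differently composed group.

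**Working it through.** **The plan's own figures.** Section [14] assumes 30% vs 10% and says: "To detect a mean difference of 20% with equal allocation to both groups would require 129 persons in total". It then says: "To allow for 33% drop-out, 194 persons will be recruited". No significance level, power or test is given, so 129 cannot be strictly reproduced. With two-sided 5% assumed and 64.5 per arm, the pooled formula gives z = (0.20 × √64.5 − 1.96 × √(2 × 0.2 × 0.8)) / √(0.3 × 0.7 + 0.1 × 0.9) = (1.606 − 1.109) / 0.548 = 0.908, a power of 81.8%. The drop-out step agrees if 33% is read as one third: 129 / (2/3) = 193.5, rounded up to 194.

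**Assumptions.** The documents give no frail share, number of levels or frailty effect. Assumed: two levels, frail share 30% or 50% (40% for the imputation), and a frailty odds ratio (OR) of 1, 2, 4 or 7 with frail people contacting less often. Stratum rates are solved so that the arm totals stay at 30% and 10%.

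**Step 1: the stratum in the primary comparison.** The stratified difference is d = Σ wₛdₛ / Σ wₛ, with wₛ = n₁ₛn₀ₛ / (n₁ₛ + n₀ₛ) (Mantel-Haenszel). Simulated trials had 130 people and permuted blocks of 8, 10 or 12 within stratum. Ranges cover both frail shares and repeated runs.

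| Frailty OR | Power change, stratified minus crude difference (points) |
|---|---|
| 1 | about 0 (−0.2 to −0.1 in the largest run) |
| 2 | 0 to +0.4 |
| 4 | +0.6 to +1.5 |
| 7 | +1.0 to +2.2 |

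The largest gain was from 85.4% to 87.6%. A separate comparison of the pooled z-test with the stratified test at 129 people gave 83.5% vs 83.6% when the frail have half the odds. At one fifth of the odds it gave 84.3–84.4% vs 85.2–85.9%. If frail people instead contact more often (30% frail), the gain in the difference analysis is +0.3, +1.4 and +2.7 points at OR 2, 4 and 7.

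With no true effect, the crude difference interval rejected in 5.2–5.6% of trials at OR 2. It fell clearly below 5% only at OR 4–7 with 50% frail. For example, at OR 7 with 20% in both arms it rejected in 4.3%, against 5.5% for the stratified interval.

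**Step 2: frailty in the imputation.** Without covariates, per-arm imputation reproduces the observed-case rate in each arm. If π is the frail share randomised, π′ the frail share among those reached, and g the non-frail minus frail contact rate in an arm, then

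bias in the difference = (π − π′) × (g intervention − g control).

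Take 40% frail.

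- With 40% of frail and 28% of non-frail people unreached: π′ = 0.40 × 0.60 / (0.40 × 0.60 + 0.60 × 0.72) = 0.240 / 0.672 = 0.357, so π − π′ = 0.043.
- With 50% and 22% unreached: π′ = 0.200 / 0.668 = 0.299, so π − π′ = 0.101.

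At OR 4 the solved rates are 40.35% and 14.47% (non-frail, frail) in the intervention arm, so g = 0.2589. In the control arm they are 14.05% and 3.93%, so g = 0.1012. The bias is 0.0429 × (0.2589 − 0.1012) = 0.0068 in the first case and 0.1006 × 0.1577 = 0.0159 in the second.

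| Frailty OR | 40% vs 28% unreached | 50% vs 22% unreached |
|---|---|---|
| 2 | 0.35 points | 0.82 points |
| 4 | 0.68 | 1.59 |
| 7 | 0.90 | 2.11 |

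If frail people contact more often, the bias turns downward and reaches about 1.0 and 2.3 points at OR 7. It is exactly zero when reach is equal (π = π′) and when the arms do not differ (equal g).

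**Step 3: both changes together.** With 194 randomised, 33% unreached at equal rates and 20 imputations per arm, power goes from 83.1% to 83.2% (OR 2), 83.4% to 84.4% (OR 4) and 83.0% to 85.0% (OR 7).

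**The case against.** The plan is silent here, not wrong. Logistic models in [20a] leave room for a frailty term, the list in [20c] is open, and the table in [12] may be only a display shell. The aim stated in [11a] is balance, which stratified randomisation delivers without any adjustment. All of that stands, so this is a point about pre-specification.

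A reader might infer that ignoring the stratum invalidates the primary test or inflates false positives. Nothing supports that: stratified allocation leaves the crude difference unbiased, and Step 1 shows no added error. Nor is the crude interval generally conservative; at weak frailty effects it rejects slightly above 5%.

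The imputation figures also deserve caution. They were computed with no covariates at all, whereas [20c] names natural teeth and last dental visit and tries a proxy first. Any correlation of those variables with frailty, or better reach through proxies, would shrink the bias. With frailty included, −0.1 to −0.4 points still remained in simulation, similar in size to the smallest bias removed.

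Finally, the change is not free of statistical cost, as set out with the fix. None of this gives a reason to leave the only stratification factor out of the written analysis.

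**Conclusion.** The point holds as a minor, cheap improvement. The design stratifies by frailty, and neither [20a] nor [20c] commits to using it. In the complete-data comparison there is no bias and no excess of false positives beyond those of the crude interval. The power forgone is negligible at a frailty OR of 2 and about 1 to 2 points at OR 4–7, if frail people contact less often. Omitting frailty from the imputation matters only if three conditions hold together: unequal reach by frailty, a frailty effect on contact, and a true arm difference. The shift is then about 0.3–1 or 0.8–2.3 points under the two reach patterns, against a planned difference of 20 points, and those sizes are probably upper-end. Every size rests on an assumed frail share, frailty effect and two levels, none of which the documents supply. A reader might also infer that [20c] excludes frailty or that the planned imputation is biased; its open list does not support either reading.

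**What to change.** In [20a], state that the primary comparison is stratified by, or adjusted for, the frailty stratum used at randomisation. One option is a Mantel-Haenszel stratified difference in proportions, with frailty also in the logistic model; the choice of method is the sponsor's. The crude table in [12] can stay as description. In [20c], add the frailty stratum to the variables in the per-arm imputation model.

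The cost is two or three sentences and a few lines of code, with these downsides:

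- **Interval calibration.** At 130 people the stratified interval is slightly anti-conservative: null rejection was 4.9–5.8% for Mantel-Haenszel and 5.3–6.0% for a standardised difference. After imputation with 194 randomised, Mantel-Haenszel gave 3.9–5.7%.
- **Sparse strata.** With 30% frail and 30% vs 10%, no frail participant has an event in 0.5%, 3.7% and 12.3% of trials at OR 2, 4 and 7. Among observed frail controls alone (97 per arm, 40% frail), none has an event in 18–62% of trials. Both the analysis and the imputation therefore need a method that tolerates zero events.
- **Very unequal reach.** With 50% vs 22% unreached, including frailty changes power by −2.5 to +2.6 points. The loss, from 84.7% to 82.2% at OR 2, is measured against a version that is biased upward.

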If we cannot reach a participant at timepoint 2, the specified proxy will be contacted. If it appears that the participant has since died, they will be considered as drop-out. If it appears that the participant is not available (e.g., due to hospitalization), we will submit the questionnaire to the proxy. When we cannot reach an individual at all, we will address this missing data by applying multiple imputation per randomization arm. We will check for having natural teeth and when the last dental visit occurred, but this is not an exhaustive list.

Methods: monitoring

[21] Data monitoring

Since this study has no major safety concerns, no data monitoring committee will be composed. No interim analysis will be conducted.

[22] Harms

An adverse event refers to an unwanted side-effect during the study, which may or may not be causally related to the intervention or other aspects of participation in the study. We expect no such events to happen because of the design of the intervention. However, participants are informed that when an injury does occur, they may contact the investigator or a member of the research team. Contact information is included in the informed consent form.

[23] Auditing

There will be no auditing.

Ethics and dissemination

[24] Research ethics approval

This study was approved by an independent Medical Ethics Committee affiliated with Ghent University Hospital and Ghent University. The study is conducted according to the guidelines for good clinical practice (ICH/GCP) and the Declaration of Helsinki established to protect people participating in clinical studies. (Reference number ONZ-2023-0350). Written informed consent will be obtained from all the participants.

[25] Protocol amendments

Any modification to the protocol of the study will need a new approval by the Medical Ethics Committee, an amendment will be requested. The decision to amend the protocol will be discussed within the research team.

[26] Consent or assent

The informed consent forms [32] were approved by the Medical Ethics Committee affiliated with the Ghent University Hospital and Ghent University. The forms are addressed to the elderly person living at home. The participants should read the informed consent forms thoroughly and discuss them with the researcher. After all questions have been answered and upon agreement, the participant should sign the forms in the space provided.

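### Harms are defined without regard to cause, but the only described way to capture them is optional participant contact about an injury, and deaths or hospital stays learned of at month 4 are not linked to it

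*Combined protocol and SAP*

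**What the plan says.** Section [22] (Harms) defines the term broadly: "An adverse event refers to an unwanted side-effect during the study, which may or may not be causally related to the intervention". It then states "We expect no such events to happen because of the design of the intervention". The one route it gives for the team to hear of an event is that "participants are informed that when an injury does occur, they may contact the investigator or a member of the research team".

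Section [20c] sets rules for participants who cannot be reached or interviewed at timepoint 2. On death: "If it appears that the participant has since died, they will be considered as drop-out". On absence: "If it appears that the participant is not available (e.g., due to hospitalization), we will submit the questionnaire to the proxy". Neither rule refers to [22].

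Section [12] describes the purpose of the month-4 contact: "Participants will be contacted 4 months after the initial contact by telephone to ask if they contacted a dental professional since the first contact". Sections [12] and [18b] provide for contact details of a partner, child or caregiver.

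On oversight, section [21] says "Since this study has no major safety concerns, no data monitoring committee will be composed", and section [23] plans no auditing.

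**The concern.** The definition and the capture route have different scopes. The definition covers effects that may be unrelated to the study. The route covers injuries only, is optional, and depends on the participant taking the first step. A participant who has died cannot use it, and one in hospital may be unable to. The team may nevertheless learn of exactly these events through the follow-up call or the proxy, and the plan then gives them no place among harms.

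Spontaneous reports would also not be comparable between arms. Only the intervention arm has an examination to which a complaint can be attributed, so the inclination to report differs by arm even if the underlying events do not.

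What is at stake is the harms statement in the trial report. If no harms are reported, a reader could not tell whether none occurred or whether none were asked about. The comparison of dental contact at 4 months is not touched.

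**Working it through.** The plan gives no harms figure to reproduce, so the main check sets the sections side by side.

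1. **Scope.** Under [22], an adverse event is one "which may or may not be causally related to the intervention or other aspects of participation in the study". The trigger for contact is an *injury*. Discomfort, upset or illness that the participant would not call an injury falls inside a cause-neutral definition but outside the trigger.
2. **Expectation.** The reason given for expecting no events is the design of the intervention. That reason bears on events caused by the intervention, not on the unrelated events that the definition also admits.
3. **Route.** [22] mentions no harms question, form, relatedness review or tabulation by arm. [12] describes the month-4 contact by its outcome question alone.
4. **Link.** [20c] handles a death as drop-out and a hospital stay as a reason for proxy response. Both are rules for non-adherence and missing data, with no onward step to [22].

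**Could such events occur in this trial?** Section [14] plans 194 participants. The documents give no 4-month risk of death or hospitalisation, so the risks below are assumptions. Expected number = 194 × risk; chance of at least one = 1 − (1 − risk)^194.

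| Event | Assumed 4-month risk | Expected number | Chance of at least one |
|---|---|---|---|
| Death | 0.5% | 194 × 0.005 = 0.97 | 62% |
| Death | 3% | 194 × 0.03 = 5.8 | over 99% |
| Hospitalisation | 2% | 194 × 0.02 = 3.9 | 98% |
| Hospitalisation | 10% | 194 × 0.10 = 19.4 | over 99% |

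Over these ranges, both arms together, at least one such event is more likely than not.

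**What could systematic questioning establish?** This is an illustration for related events only.

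- Intervention arm under 1:1 allocation: 194 / 2 = 97.
- Reached, if the full 33% drop-out allowance in [14] is used up: 97 × (1 − 0.33) = 65.
- Exact one-sided 95% upper limit for 0 of 65: 1 − 0.05^(1/65) = 4.5%.
- With no drop-out, 0 of 97: 1 − 0.05^(1/97) = 3.0%.

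Both limits assume that everyone reached had the examination. Section [11b] allows for refusals, which would shrink the denominator and raise the limit. With spontaneous injury reports alone, the number effectively asked is unknown and no limit can be calculated.

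**The case against.** The strongest reply is proportionality. The intervention is a single oral examination with head lamp, mirror and periodontal probe, without x-rays, plus counselling, letters and leaflets. An ethics committee approved the study, any immediate problem would arise in front of the researcher, and the primary analysis does not depend on harms. This stands, and it is why the importance is low.

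The wording of [22] is also less clear than the contrast above suggests. It says *side-effect*, which implies a cause, and then says the cause may be absent. It is therefore not certain that every unrelated death or hospital stay was meant to count. This stands too; the definition itself needs settling.

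A reader might go further than the documents allow in four ways:

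- **That deaths and hospital stays will never be recorded.** This would be an inference from silence. A death is recorded, as drop-out. The appendix questionnaire was not available, and [20c] calls the month-4 instrument a questionnaire, so it may hold more than the outcome item.
- **That the plan expects to learn of such events.** [20c] is conditional, and hospitalisation is only its example of unavailability.
- **That the protocol itself names psychological harms of the check-up.** In [6a], shame is a consequence of poor oral health, distress describes oral health status, and fear of the dentist is a reason for avoiding care. None is presented as an effect of the examination.
- **That [30] announces a safety conclusion.** It states an expectation, to explain why no ancillary or post-trial care is arranged. Section [31] says results go to the Flemish Government and says nothing of wider use.

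**Conclusion.** The point holds in a limited form. As described, [22] pairs a cause-neutral definition with a self-initiated, injury-only route, and [20c] leaves deaths and hospitalisations learned of at month 4 unconnected to harms. An absence of reported harms would then be uninterpretable and not comparable between arms.

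The importance is low: sample size, primary outcome and its analysis are unaffected. The finding rests on the text of [12], [20c] and [22]. If the appendix questionnaire already contains a harms item, citing it in [22] would settle that part, and the link from [20c] and the reporting by arm would remain to be added. The event counts rest on assumed risks. The 4.5% limit is illustrative: it concerns related events, not unrecorded deaths or hospital stays, and it assumes the full 33% drop-out and that every intervention participant reached was examined.

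**What to change.** In the timepoint-2 REDCap form, after the primary outcome is saved and with identical wording in both arms:

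- **(a)** Ask one neutral question that does not require the respondent to attribute a cause, for example whether there has been any unwanted or upsetting effect or health problem since the first contact. A question limited to problems linked to the study would keep the imbalance between arms.
- **(b)** Log any death or hospitalisation learned of from the participant or the proxy, alongside the existing handling in [20c].

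In [22]:

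- Align the side-effect definition with the injury trigger, so that one scope applies to both.
- State that solicited and spontaneous reports are reviewed for relatedness and tabulated by arm, with the number actually questioned as denominator.
- Limit the statement that no events are expected to intervention-related events.

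The cost is about a minute on a contact already planned for everyone, and an ethics amendment under [25]. An answer may reveal the arm to the caller, whom [17] intends to be unaware of it; asking after the outcome is saved protects that outcome. Participants whom neither the call nor the proxy reaches remain uncovered, which the denominator should show.
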